#### 4.3.2.3.2. *Time to Defervescence*

Summary statistics of time to defervescence assessed up to 29 days, if possible, will be presented by treatment group. Time to defervescence is defined as the time (in days) from initiation of study treatment (favipiravir + SOC or SOC alone) until normalization of fever, described as an oral temperature  $\leq 37.2$  °C, or discharge. Only subjects with fever at study entry or within the first 72 hours will contribute to this analysis.

A Kaplan-Meier curve will be provided for the overall ITT population, where subjects will be censored at the last assessment of the parameter if no defervescence is observed.

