 - i. Fever ≤ 37.2 °C oral,
 - ii. Respiratory rate ≤ 24 /minute on room air,
 - iii. Oxygen saturation SpO2 > 94% on room air,
 - iv. Cough mild or absent on a patient reported scale of severe, moderate, mild, absent.
- 3. Clinical effect as measured by the National Early Warning Score 2 (NEWS2) system.
- 4. All-cause mortality as assessed daily up to 29 days and at final follow up on Day 60.
- 5. Frequency of respiratory progression as assessed up to 29 days (daily and per SOC at each site) and defined as:
 - a. SpO2 \leq 94% on room air or PaO2/FiO2 \leq 300mmHg, and
 - b. requirement for supplemental oxygen, or
 - c. more advanced ventilator support.
- 6. Time to defervescence (in those with fever at enrollment) as assessed daily up to 29 days and at Day 60 (if possible).
- 7. Time to cough reported as mild or absent (in those with cough at enrollment rated severe or moderate) as assessed daily up to 29 days and on Day 60.
- 8. Time to dyspnea reported as mild or absent (on a scale of severe, moderate, mild absent, in those with dyspnea at enrollment rated as severe or moderate) as assessed daily up to 29 days and on Day 60 (if possible).
- 9. Frequency of requirement for supplemental oxygen or non-invasive ventilation as assessed daily up to 29 days and on Day 60.
- 10. Time to SARS-CoV-2 RT-PCR negative in upper respiratory tract specimen as assessed up to 29 days.
- 11. Change in SARS-CoV-2 viral load in upper respiratory tract specimen as assessed by area under viral load curve as assessed up to 29 days.
- 12. Frequency of requirement for mechanical ventilation as assessed up daily to 29 days and at Day 60
- 13. Safety of favipiravir + SOC v. SOC alone as assessed daily up to 29 days and at Day 60.
- 14. C-reactive protein (CRP) over time.
- 15. Population PK analysis of favipiravir with assessment of maximum plasma concentration (C_{max}), minimum plasma concentration (C_{min}), and AUC_(0-24h) on Days 1, 2, 8 and 14.

Study Sites	Approximately 8 sites in the U.S.A.
Planned Enrollment	Approximately 50 subjects; randomized 1:1
Study Population	Adults who are hospitalized for treatment of confirmed COVID-19

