9.2 Sample size justification

Approximately 50 subjects will be enrolled. The primary endpoint analysis will consist of a log-rank test of the difference in treatment groups in the time to viral clearance. Based on a recent publication:

(https://www.sciencedirect.com/science/article/pii/S2095809920300631?via%3Dihub)

it is assumed that the median time to clearance for favipiravir would be approximately 4 days, and the median time for SOC would likely be approximately 11 days; this latter estimate may in fact be conservative since SOC is not as likely to reduce viral load as well as the control in the above referenced study. Using two-sided alpha of 0.10 and power of 90% (appropriate for a trial to be used as the justification for a confirmatory, fully-powered blinded and randomized Phase 3 study), and a fixed per-subject observation period of 15 days, an approximate sample size of 25 subjects per arm (total size of 50) would be required.

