**Table 4-1 Normalization and Alleviation Criteria**

| Parameter         | Criteria   |
|-------------------|--|
| Fever             | $\leq 37.2$ °C   |
| Respiratory Rate  | $\leq 24$ breaths/minute on room air   |
| Oxygen Saturation | SpO 2 > 94% on room air   |
| Cough             | Mild or absent on a subject-reported scale of severe, moderate, mild, absent |

Subjects with no evidence of clinical recovery will be censored at last assessment of the parameter that is not be recovered. The censoring rules as provided in Section 4.3.1 will also be employed. In addition, if a subject achieves TTCR and then discontinues from the study during the 72 hour confirmation period, it will be censored at the discontinuation. If a subject achieves TTCR and then discharge, it will be confirmed as recovered at the time of achieving TTCR.

The difference between treatment groups will be analyzed using a log-rank test at the two-sided alpha level of 0.10, where the p-value will be presented for descriptive purposes (and using a stratified log-rank test by disease severity as a sensitivity analysis).

Analyses of TTCR will be done on the ITT population. Only patients with at least one abnormal result (among the four symptoms listed in Table 4-1) at baseline (or within 72 hours post baseline) will be included in the analysis.

Kaplan-Meier curves will be provided for the overall ITT population. By-subject data listings will also be provided.

In addition, the analysis will be performed with stratification by disease severity.

The analysis will also be repeated by the dexamethasone usage subgroup, where patients will be categorized as having received dexamethasone if they received it at any time prior to the last assessments of normalization and alleviation criteria.

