#### 4.3.2.4. Analysis of the National Early Warning Score

The time to aggregate NEWS2 score of  $\leq 2$  (sustained for at least 72 hours) or hospital discharge will be analyzed up to Day 29 in a similar manner as the time to TTCR described in [Section 4.3.2.2](#). Only patients with a score  $>2$  at baseline or within 72 hours post baseline will contribute to the analysis. Subjects will be censored at last assessment of the parameter if there are no events of  $\leq 2$  aggregate scores. The censoring rules as provided in Section 4.3.1 will also be employed. In addition, if a subject achieves the event and then discontinues from the study

during the 72-hour confirmation period, it will be censored at the discontinuation. If a subject achieves the event and then discharge, it will be confirmed as reach the event at the time of aggregate NEWS2 score of  $\leq 2$ ; Kaplan-Meier curves will be provided for the overall ITT population.

In addition, the analysis will be performed with stratification by disease severity.

Additionally, descriptive statistics of mean changes from baseline in aggregate NEWS2 scores to post-baseline visits will be provided by treatment group. This analysis will be performed using the ITT population. Only patients with at least one-post baseline measurement will be included.

By-subject data listings will be provided.

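### Five secondary analysis sets admit subjects who first become abnormal up to 72 hours after baseline, so they select on an event that treatment can affect and leave some event times unclear

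*SAP*

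**What the plan says.** **Protocol.** The Synopsis restricts three symptom endpoints by status at entry. Endpoint 6 reads "Time to defervescence (in those with fever at enrollment) as assessed daily up to 29 days", and endpoints 7 and 8 are limited to subjects whose cough or dyspnea was moderate or severe at enrollment. TTCR (endpoint 2) carries no such restriction. NEWS2 (endpoint 3) is named only as a measure of clinical effect, with no subset and no time-to-event definition.

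**SAP.** All five analyses use a wider window:

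- Fever (4.3.2.3.2): "Only subjects with fever at study entry or within the first 72 hours will contribute to this analysis". Sections 4.3.2.3.3 and 4.3.2.3.4 use the same rule for moderate or severe cough and dyspnea.
- TTCR (4.3.2.2, below Table 4-1): patients with at least one of the four criteria abnormal "at baseline (or within 72 hours post baseline) will be included in the analysis".
- NEWS2 (4.3.2.4): patients scoring above 2 "at baseline or within 72 hours post baseline will contribute to" the time-to-event analysis.

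SAP 3.5 starts the clock at first dose for favipiravir and at randomization for SOC. It also lets the SOC baseline be the measurement closest to randomization, before or after it. The analyses are described as ITT. SAP 3.2 makes every p-value other than the primary's descriptive. SAP Section 5 lists one change from the protocol, the removal of hierarchical testing.

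**The concern.** A subject who is normal at time zero enters these sets only by becoming abnormal in the next 72 hours. If favipiravir affects early onset, the drug partly decides who is compared. A favipiravir subject kept normal is dropped, while a similar SOC subject who worsens is included. The sets are then no longer the randomized groups, although the analyses are called ITT.

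The clock is a second problem, and it exists even if onset is equal in both arms. TTCR and NEWS2 require a state sustained for 72 hours, so a late-onset subject cannot have the event at time zero, and the recorded time includes up to 3 days before onset. The defervescence section states no sustained-duration rule of its own. A subject who is afebrile at time zero and febrile on Day 3 already meets the 37.2 °C criterion at the start. SAP 4.3.2.3 refers to the TTCR methodology in general terms but does not settle this.

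With descriptive p-values, the estimates carry the weight. Protocol 9.1 wants them to support a Phase 3 trial. The second secondary objective (Protocol 4.2) uses clinical recovery, fever, cough and dyspnea to judge whether the ordinal scale could serve as a primary endpoint.

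**Working it through.** **1. The plan's own figure.** The documents give no expected size for these sets. The only design figure is 25 per arm, used below. Protocol 9.2 assumes "the median time to clearance for favipiravir would be approximately 4 days" and "the median time for SOC would likely be approximately 11 days", with "a fixed per-subject observation period of 15 days", two-sided alpha 0.10 and 90% power. The hazard ratio is 11/4 = 2.75. Exponential event probabilities by Day 15 are 0.926 and 0.611, mean 0.769. Freedman's formula gives 39.3 events, and 39.3/0.769 = 51.2, so 52 subjects. Power at 50 is 0.894. The figure reproduces, and this point does not depend on it.

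**2. Set against set.**

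| Endpoint | Protocol | SAP | In SAP Section 5? |
|---|---|---|---|
| Fever, cough, dyspnea | affected at enrollment | at entry or within 72 h | no |
| TTCR | no restriction | abnormal at baseline or within 72 h | no |
| NEWS2 | no set defined | above 2 at baseline or within 72 h | no |

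**3. Expected set sizes.** The documents give neither the proportion abnormal at baseline nor the onset rate, so both are assumed. Let b be the proportion abnormal at baseline and q the onset by 72 hours among the rest. The expected set per arm is 25 × [b + (1 − b)q]. With b = 0.40, the enrollment rule gives 10 per arm. The 72-hour rule gives:

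- q = 15% favipiravir v 40% SOC: 10 + 15 × 0.15 = 12.25 v 10 + 15 × 0.40 = 16.
- q = 10% v 60%: 11.5 v 19.

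Over a wider range (b from 30% to 70%, q of 10% on favipiravir and 30-50% on SOC), the sets are 9.25-18.25 v 12.75-21.25. Late-onset subjects form 4-19% of the favipiravir set and 11-54% of the SOC set. Equal q keeps the sets balanced.

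**4. Effect on the estimate, late-onset time counted from time zero.** Assume exponential symptom duration with median 4 days in both arms (λ = ln 2/4 = 0.1733) and onset uniform over 0-3 days. Discharge is not modelled. If p is the late-onset share of a set, then for t ≥ 3 days:

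S(t) = e^(−λt) × [1 + p(k − 1)], with k = (e^(3λ) − 1)/(3λ) = 0.6818/0.5199 = 1.311.

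The median is 4 + ln(1 + 0.311p)/λ.

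- 15% v 40%: p = 2.25/12.25 = 0.184 v 6/16 = 0.375. Medians are 4.32 v 4.64 days.
- 10% v 60%: p = 1.5/11.5 = 0.130 v 9/19 = 0.474. Medians are 4.23 v 4.79 days.

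After Day 3 the hazard is λ in both arms, so the whole difference arises in the first 3 days. Simulated log-rank rate ratios (favipiravir to SOC) under no true effect are as follows. The lower figure of each pair has uniform onset; the higher has onset on whole days 1-3.

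| Onset, favipiravir v SOC | Rate ratio |
|---|---|
| equal | about 1.00 |
| 25% v 30% | about 1.01 |
| 15% v 40% | 1.05-1.06 |
| 10% v 60% | 1.10-1.12 |

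The enrollment-only rule gives about 1.0 throughout.

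**5. Direction.** If late-onset subjects are instead given their event at time zero, a possible literal reading of 4.3.2.3.2, the ratios become about 0.79 (15% v 40%) and 0.66 (10% v 60%). A separate simulation with longer symptom duration, b = 30% and onset of 10% v 40% gave medians of 5.9 (favipiravir) v 6.3 (SOC) days. When the drug prevented onset only in milder subjects, this became 6.4 v 6.0 days.

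**6. Against the noise.** With 12.25 v 16 subjects, all with events, the standard error of the log rate ratio is √(1/12.25 + 1/16) = 0.38. ln(1.06) = 0.058 is 0.15 of that. With 11.5 v 19 it is 0.37, and ln(1.12) = 0.113 is 0.30 of it. Simulated rejection rates at nominal 10% with 25 per arm were 10.5-13% under the 72-hour rule and 10-13% under the enrollment rule.

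**The case against.** The 72-hour window is not arbitrary. TTCR and NEWS2 events must be sustained for 72 hours, so a subject normal at baseline who worsens within that time has not reached the endpoint at time zero, while one who stays normal has. The rule removes the second kind and keeps the first. It also yields larger sets in a 50-subject trial. This explains the rule, but membership still turns on a post-treatment event.

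The stakes are also limited. The study is exploratory, the p-values are descriptive, by-subject listings allow re-analysis, and SAP Section 5 promises that changes will be summarized in the study report. The larger rate ratios need a very strong drug effect on onset within 3 days, and every onset rate is assumed. All of this stands, and it bounds the importance of the point.

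A reader might infer that all five sets depart from an enrollment rule in the protocol. They do not: only fever, cough and dyspnea have one. Restricting TTCR to subjects abnormal at baseline would itself differ from the protocol.

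**Conclusion.** The point holds as a selection and definition problem in five secondary analyses. Three sets contradict the protocol, TTCR gains a restriction that the protocol lacks, and the NEWS2 set is new. None of these is declared in SAP Section 5.

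It is tempting to conclude that the rule makes favipiravir look better. The documents do not support that. The sign depends on whether and in whom the drug changes early onset, and on how a late-onset event time is read. Under the assumptions in the working, with time counted from time zero, the distortion is 0-12% on the rate ratio and small against the sampling error. The time-zero reading gives larger shifts the other way, which is a reason to settle the definition. Nor does the point touch the primary endpoint or the proof-of-concept test. The change is worth making because it is cheap and because a bias of unknown sign cannot be corrected afterwards.

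**What to change.** - Define the fever, cough, dyspnea and NEWS2 sets by status at the last measurement before treatment start (favipiravir) or before randomization (SOC). The SOC part matters because SAP 3.5 lets that arm's baseline fall after randomization.
- For TTCR, use all ITT subjects as in the protocol, or a subset abnormal before treatment, listed as a change.
- Keep the 72-hour set only as a labelled sensitivity analysis, and state there how the event time of a subject normal at time zero is determined.
- Report the number with new onset within 72 hours by arm.
- List the changes in SAP Section 5.

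The cost is wording in five SAP subsections and smaller sets. The loss is not always slight: in the two scenarios above the SOC set falls from 16 to 10 (38%) or from 19 to 10 (47%). It is small if early onset is rare.

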#### 4.3.2.3.3. *Time to Mild/Absent Cough*

Time to mild/absent cough will be analyzed in a similar fashion to time to defervescence. Only subjects with reported moderate or severe cough at study entry or within the first 72 hours will contribute to this analysis. Subjects will be censored at the last assessment of the parameter if no mild/absent cough is observed.

#### 4.3.2.3.4. *Time to Mild/Absent Dyspnea*

Time to mild/absent dyspnea will be analyzed in a similar fashion to time to defervescence. Only subjects with reported moderate or severe dyspnea at study entry or within the first 72 hours will contribute to this analysis. Subjects will be censored at the last assessment of the parameter if no mild/absent dyspnea is observed.

#### 4.3.2.3.5. *ECOG Performance Status*

ECOG performance status will be tabulated over time by treatment group.

#### 4.3.2.4. Analysis of the National Early Warning Score

The time to aggregate NEWS2 score of  $\leq 2$  (sustained for at least 72 hours) or hospital discharge will be analyzed up to Day 29 in a similar manner as the time to TTCR described in [Section 4.3.2.2](#). Only patients with a score  $>2$  at baseline or within 72 hours post baseline will contribute to the analysis. Subjects will be censored at last assessment of the parameter if there are no events of  $\leq 2$  aggregate scores. The censoring rules as provided in Section 4.3.1 will also be employed. In addition, if a subject achieves the event and then discontinues from the study

during the 72-hour confirmation period, it will be censored at the discontinuation. If a subject achieves the event and then discharge, it will be confirmed as reach the event at the time of aggregate NEWS2 score of  $\leq 2$ ; Kaplan-Meier curves will be provided for the overall ITT population.

In addition, the analysis will be performed with stratification by disease severity.

Additionally, descriptive statistics of mean changes from baseline in aggregate NEWS2 scores to post-baseline visits will be provided by treatment group. This analysis will be performed using the ITT population. Only patients with at least one-post baseline measurement will be included.

By-subject data listings will be provided.

#### 4.3.2.5. Reduction in Oxygen/Ventilation Requirements

The frequency of requirement for any supplemental oxygen or ventilation (non-invasive, mechanical, or ECMO), as assessed daily up to 29 days and on Day 45 and 60, if possible, will be analyzed in a similar fashion as respiratory progression in [Section 4.3.2.3.1](#).

In addition, the frequency of requirement for any ventilation requirement (non-invasive, mechanical or ECMO) and either mechanical ventilation or ECMO will be analyzed in the same manner as above.

The analyses on oxygen/ventilation requirements will be performed using the ITT population.

#### 4.3.2.6. Duration of Supplemental Oxygen, Non-Invasive Ventilation, Mechanical Ventilation, ECMO, Hospitalization, and Time in ICU

The total duration (in days) of any respiratory assistance (supplemental oxygen, non-invasive ventilation, mechanical ventilation, ECMO), hospitalization, and ICU will be analyzed using an ANCOVA model, investigating the difference in means between the treatment groups. The difference in mean durations between treatment groups will be provided, along with 90% CI. All durations are counted from randomization. In addition, the total time on any ventilation assistance (non-invasive/mechanical ventilation, ECMO), and either mechanical ventilation or ECMO will be analyzed using an ANCOVA model as above.

The exact duration will be counted. But, it was initiated prior to study enrollment, duration will be calculated from treatment start date for patients on favipiravir and randomization date for patients on SOC. The maximum value of these durations will not exceed 60 days

The analyses above will be performed using the ITT population.

Box plots for the total duration of any respiratory assistance and hospitalization will be provided by treatment group. By-subject data listings for each parameter will also be provided.

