### **3.7. Adjustments for Covariates**

For the analyses of durations of supplemental oxygen, non-invasive/mechanical ventilation, Extracorporeal Membrane Oxygenation (ECMO), hospitalization, and ICU, baseline SpO2 level will act as a covariate in all analysis of covariance (ANCOVA) models. Disease severity, as defined in [Section 1.2.2](#), will be accounted for in all efficacy analyses. Other factors may be accounted for if deemed relevant.

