### **4.3. Efficacy Evaluation**

#### **4.3.1. Analysis of the Primary Efficacy Endpoint**

The primary endpoint of time to viral clearance will be analyzed with the log-rank test for treatment difference based on a two-sided alpha-level of 0.10 and summarized using Kaplan-Meier methodology. The time to viral clearance (in days) is defined as the time of Negative or Lower Limit of Quantification (LLOQ) results (without any quantitative results after that) as measured by PCR for SARS-CoV-2 via scheduled nasopharyngeal and oropharyngeal swab samples minus the date of first dose + 1.

Subjects who have no evidence of viral clearance will be censored at the time of the last PCR measurement with the following conditions:

- Patients whose symptoms worsen (defined as an increase of  $\geq 1$  point on the 6-point Ordinal Scale from baseline) on the day of the last PCR measurement, or who die will be censored at Day 29,
- Patients who are lost to follow-up will be censored on the day of the last PCR measurement.

The median time to viral clearance will be estimated based on the Kaplan-Meier estimator; additional summary statistics will be presented, including the 25th and 75th percentiles, 90% CIs (the log-log transformation) on the median and other percentiles and proportion of censored subjects. Viral clearance rates at Days 3, 8, 11, 15, and 29 will also be presented.

The analysis of the primary efficacy endpoint will be done using the ITT population.

The primary analysis will be supplemented with a sensitivity analysis, using a stratified log-rank test, where the treatment difference based on a two-sided alpha-level of 0.10 will be summarized and stratified by disease severity.

The analysis will also be repeated by the dexamethasone usage subgroup, where patients will be categorized as having received dexamethasone if they received it at any time prior to the last viral clearance assessment.

Kaplan-Meier curves will be provided for the overall ITT population. By-subject data listings of viral clearance data will also be provided.

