#### 4.3.2. Analysis of Secondary Efficacy Endpoints

##### 4.3.2.1. Analysis of Clinical Status via the Study-Specific 6-point Ordinal Scale

The first secondary endpoint of clinical status as measured by the study-specific 6-point ordinal scale at Day 15 will be analyzed by fitting a cumulative odds model, using the most appropriate approach. Clinical status will be modelled as the dependent variable (ordered from 1 to 6, as defined in [Section 1.2.6.1](#)), and treatment group and disease severity as independent variables; other factors may be added for exploratory purposes. Subjects with missing Day 15 data will have their clinical status imputed in the following manner:

- 1) If patients were discharged prior to Day 15, then their clinical status will be imputed to 'Not Hospitalized' at Day 15
- 2) If patients died prior to Day 15, then their clinical status will be imputed to 'Death' at Day 15
- 3) If there is no evidence of hospital discharge or death, clinical status at Day 15 will be imputed using the multiple imputation method described in [Section 3.10.1](#)

The odds ratios and their 90% CI will be provided. As described in [Section 3.2](#), a test at the two-sided alpha level of 0.10 will be performed for descriptive purposes.

Longitudinal analysis of the 6-point scale over time at each visit will be performed in a similar manner. Clinical status will be modelled as the dependent variable and treatment group, disease severity, visit, and the visit/treatment group interaction term as independent variables. The overall treatment odds ratio and their 90% CI will be provided, along with by-visit odds ratios and 90% CI.

Analyses using the study-specific 6-point scale will be done using the ITT population.

The analysis will also be repeated by the dexamethasone usage subgroup, where patients will be categorized as having received dexamethasone if they received it at any time prior the Day 15 analysis visit assessment.

Stacked bar charts over time will be generated to graphically display the proportion of patients in each level of the 6-point scale by treatment group for the ITT population.

By-subject data listings will be provided.

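### The duration analyses in SAP 4.3.2.6 have no rule for death, so an early death counts as a short, favourable duration

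*SAP*

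**What the plan says.** SAP 4.3.2.6 takes the total days on any respiratory assistance, in hospital and in ICU, and compares the arms by a difference in mean duration with a 90% CI: the durations of "hospitalization, and ICU will be analyzed using an ANCOVA model, investigating the difference in means between the treatment groups". On counting it says "The exact duration will be counted" and "The maximum value of these durations will not exceed 60 days". On population it says "The analyses above will be performed using the ITT population", so subjects who die are included.

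The means are adjusted. SAP 3.7 states that baseline SpO2 "level will act as a covariate in all analysis of covariance (ANCOVA) models" and that disease severity "will be accounted for in all efficacy analyses".

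The section does not mention death. Other sections of the SAP do:

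- **4.3.1 (viral clearance):** subjects without clearance whose symptoms worsen "or who die will be censored at Day 29". The 4.3.1 censoring rules are carried over to time to clinical recovery (4.3.2.2) and time to a low NEWS2 score (4.3.2.4).
- **4.3.2.1 (Day 15 ordinal scale):** "If patients died prior to Day 15, then their clinical status will be imputed to 'Death' at Day 15", which is the worst category.
- **4.3.2.1.1 (ordinal-scale sensitivity analysis):** a subject who has died adds nothing at later timepoints.

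None of these rules is extended to durations.

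**The concern.** Death ends every one of these counts. A subject who dies in hospital on Day 6 contributes about 6 hospital days, and a survivor discharged on Day 12 contributes about 12. Where a shorter duration reads as better, the death has the better score.

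The mean difference therefore mixes two things: faster recovery, which should shorten durations, and early death, which shortens them as well. The more early deaths an arm has, the better it looks. Conversely, a treatment that keeps some very ill subjects alive can be shown with longer mean support or stay. Deaths are foreseeable here, since randomization has a critical-disease stratum and all-cause mortality is a listed secondary endpoint. A reader of the study report could take a difference in mean stay as evidence on recovery when part of it reflects who died and when.

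**Working it through.** **Does another section supply a rule?** SAP 3.10.1 imputes missing post-baseline visit values under missing at random and does not mention death. A duration ended by death is observed, so nothing is missing to impute. The 60-day limit in 4.3.2.6 is an upper bound, not a value assigned to deaths. Protocol 9.6 names worst-value assignment among its methods for missing clinical outcomes and leaves the detail to the SAP, which does not apply it to durations. As written, a death enters at its observed length.

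**Does the covariate adjustment help?** No. SpO2 and severity are measured at baseline. They balance the arms at entry but do not change the outcome recorded for a subject who later dies.

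**Inputs.** SAP 3.1 gives n = 25 per arm, and 4.3.2.6 gives the 60-day limit. The documents state no figure for the duration analyses that could be reproduced, and no mortality rate or length of stay. Assumed therefore: k deaths averted on favipiravir, each on day t under SOC, each with a stay of s days if saved, and arms otherwise identical. Covariates are ignored.

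**As written.** The k subjects contribute t days each in one arm and s days each in the other, so

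favipiravir minus SOC = k(s − t)/25.

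**With deaths scored at the 60-day maximum.** Replace t by 60: k(s − 60)/25, which does not depend on the day of death.

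| k | t | s | As written (days) | Deaths scored 60 (days) |
|---|---|---|---|---|
| 1 | 6 | 15 | 9/25 = +0.36 | −45/25 = −1.80 |
| 1 | 6 | 25 | 19/25 = +0.76 | −35/25 = −1.40 |
| 1 | 6 | 40 | 34/25 = +1.36 | −20/25 = −0.80 |
| 3 | 6 | 40 | 102/25 = +4.08 | −60/25 = −2.40 |
| 2 | 10 | 25 | 30/25 = +1.20 | −70/25 = −2.80 |
| 1 | 15 | 15 | 0 | −45/25 = −1.80 |
| 3 | 15 | 8 | −21/25 = −0.84 | −156/25 = −6.24 |

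A positive value makes favipiravir look worse. For k from 1 to 3, t of 6, 10 or 15 and s from 8 to 40, the result as written runs from −0.84 to +4.08 days. It is positive when s exceeds t, zero when they are equal, and negative when s is smaller.

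**When others also recover faster.** In the row k = 2, t = 10, s = 25, the rescued subjects add 30 days in total. An average shortening of 30/23 = 1.3 days in the other 23 subjects of the arm would cancel that.

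**Simulation, all inputs assumed and unadjusted for covariates.** Median death on day 10, median stay 25 days if saved and 9 days in other survivors:

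| Mortality, SOC v. favipiravir | Shortening of stay | Mean difference (days) | Trials with favipiravir longer |
|---|---|---|---|
| 20% v. 10% | none | +1.58 | 76% |
| 20% v. 10% | 10% | +0.41 | 58% |
| 20% v. 10% | 20% | −0.68 | 36% |
| 5% v. 2.5% | none | +0.37 | 57% |

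With no treatment effect at all, about 50% would be expected by chance.

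**The case against.** The case for leaving the section alone has several parts.

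- **Standing of the analysis.** The durations are not among the protocol's 15 numbered secondary endpoints; they appear only as measurements in the synopsis and in protocol 8.1. SAP 3.2 makes every p-value other than the primary one descriptive. This stands and limits the impact.
- **Mortality is visible.** SAP 4.3.2.7 gives a severity-stratified relative risk for all-cause mortality, and listings of deaths and durations are planned. This also stands, but a mortality table does not correct the duration estimate printed near it.
- **The shift is small against the noise.** If the SD of stay is 8 to 15 days (an assumption), the 90% CI half-width at 25 per arm is 1.677 × SD × √(2/25), or about 3.8 to 7.1 days. One averted death moves the mean 0.4 to 1.4 days. This is fair, but the shift is systematic and a wide interval does not remove it.

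A reader might also infer more than the documents support:

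- **That the means are raw.** They are not; SAP 3.7 adjusts for baseline SpO2 and severity.
- **That the SAP penalises death everywhere else.** It does not; the sensitivity analysis in 4.3.2.1.1 simply drops subjects after death.
- **That the first secondary objective is compromised.** Protocol 4.2 assesses that objective on the 6-point scale, where death is the worst category. Protocol 9.1 rests proof of concept on viral clearance, and the candidate clinical endpoint for a later trial is the ordinal scale. Nothing in the documents makes the next trial depend on durations.

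**Conclusion.** The point holds as a gap worth closing in a descriptive secondary analysis. Following SAP 4.3.2.6 as written, an early death is scored as a short duration, and the estimated difference is pulled in favour of the arm with more early deaths.

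It would go too far to say that a life-saving effect will look like harm. That happens only if rescued subjects stay longer than the time to death and this is not outweighed by shorter stays in other survivors. If rescued stays are short, the sign goes the other way.

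With 25 per arm, death on Day 6 and stays of 15 to 40 days if saved, the size is 0.4 to 1.4 days per death averted. These inputs are illustrative. The primary analysis and the Day 15 ordinal-scale analysis are not affected.

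**What to change.** In SAP 4.3.2.6:

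1. Make the main between-arm comparison the number of days alive and free of each support, hospital or ICU through Day 60, with death by Day 60 scored as 0 free days. This is equivalent to giving deaths the SAP's own 60-day maximum. Compare the arms with a severity-stratified rank test.
2. State how unknown Day 60 status is handled. SAP 4.1 defines study completion at Day 29, so some subjects may lack it.
3. Keep the planned ANCOVA mean durations with their 90% CIs as a supplementary description, with the number of deaths per arm beside them.
4. Label any survivors-only summary as conditioned on a post-randomization outcome.

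The cost is SAP wording and programming. Date of death and the periods of respiratory assistance, hospitalization and ICU are already listed for collection in SAP 1.2.6.1.

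The downside is that the measure becomes a composite with death. For ventilation, ECMO and ICU, where many subjects may have no days at all, it may largely reflect mortality. The rank test also gives up the SpO2 covariate, which is one reason to keep the ANCOVA alongside.
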